1.1. Study Rationale

In this trial, we propose the combination of systemic therapy with nirogacestat and cryoablation to maximize the benefits of both modalities for subjects with growing or symptomatic desmoid tumors. It is hypothesized that the combination will provide long-lasting disease control and a quick time to treatment response.

This phase 2 study will enroll participants \geq 18 years of age. The pharmacokinetics (PK) and optimal dosing of nirogacestat in younger participants has not been established.

Treatment will consist of a 3-month lead-in period of nirogacestat, followed by cryoablation procedure (single treatment), followed by continued nirogacestat treatment for up to a total of 24 months (maximum 26 cycles of treatment), unless disease progression or one of the criteria in Section 3.7 (Subject Study Completion or Termination) occurs. The lead-in period will allow assessment of the response to nirogacestat-alone and potentially lead to improved cryoablation success if there is tumor shrinkage.

In order to assess increased efficacy of combination therapy over single-modality cryoablation, results will be compared to historical data from the Stanford existing cryoablation population treated at Stanford. For these subjects, two-thirds are unable to be completely ablated and most of those patients will have clearly recurrent disease at 6 months. Therefore, we hypothesize that adding on nirogacestat to cryoablation will lead to an 80% clinical benefit rate at 1 year.

Nirogacestat alone has a RECIST response of 29% of patients at a median of 24 months.¹ At 1 year, the ORR was 2 of 17 (12%).

To evaluate effects of cryoablation plus nirogacestat on quality of life (QOL), we will collect patient-reported outcome (PRO) measures using the EQ-5D-3L.

To remain consistent with prior inclusion criteria for desmoid trials, we will only include subjects with growing or symptomatic desmoid tumors. In addition, we will standardize the cryoablation procedure by limiting subjects to 1 cryoablation treatment session at time of intervention and desmoid tumors that can be at least 50% treated with cryoablation but are $<$ 75% cryoablitable.

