An investigator-initiated phase 2, open-label, single-center study was sponsored and conducted by the National Cancer Institute (NCI) to evaluate the objective response rate (ORR) after therapy with nirogacestat in subjects with recurrent, refractory, progressive desmoid tumors (Kummar et al., 2017). 17 subjects received daily doses of nirogacestat at the RP2D of 150 mg BID continuously in 3-week cycles. Response to treatment was evaluated at Cycle 1 and every 6 cycles (18 weeks) thereafter by RECIST v1.1. Of the 17 subjects treated in the study, 15 had mutations in APC or CTNNB1 genes. 16 subjects were evaluable for response with 5 (29%) subjects achieving PR after a median of 32 cycles (96 weeks) of nirogacestat. The remaining 11 subjects had a best response of stable disease (SD) and no instances of progressive disease were observed. All but 1 evaluated subject had a measurable regression of tumor volume by MRI. The AE profile was consistent with previous reports (Messersmith, et al., 2015; Kummar et al., 2017) and consisted of all subjects experiencing at least one TEAE with the majority being Grade 1 to 3. The most frequently ($\geq 70\%$) reported TEAEs were diarrhea (88%), headache (76%), hypophosphatemia (76%), AST increased (71%), lymphocyte count decreased (71%), and nausea (71%). A total of 10 (59%) subjects reported Grade 3 treatment-related TEAEs. Eight (47%) subjects reported Grade 3 hypophosphatemia, 1 (6%) subject reported Grade 3 diarrhea, 1 (6%) subject reported Grade 3 fatigue, and 1 subject (6%) reported Grade 3 menstruation irregular. Per the sponsor, the subject that reported the Grade 3 menstruation irregular TEAE was postmenopausal prior to enrolling in the study, and thus this event should not have been reported as a TEAE. A total of 9 (53%) subjects reported at least one SAE including 4 (24%) subjects reporting events considered by the investigator to be related to nirogacestat. No SAE was reported in more than one subject. The 4 SAEs that were considered by the investigator to be related to nirogacestat were blood bilirubin increased, hypersensitivity, squamous cell carcinoma, and vulvovaginal inflammation, which were each reported in a single subject. All related SAEs were reported as Grade 2 severity. A single event of Grade 2 hypersensitivity, considered by the investigator to be possibly related to study treatment, led to the permanent discontinuation of study treatment in one subject. There was one death on study due to a cerebrovascular accident that was assessed by the investigator to be unlikely related to nirogacestat. There were no TEAEs that were considered to be DLTs.

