1.3.3. Known Potential Benefits

We hypothesize that the combination of systemic therapy with nirogacestat and cryoablation will provide longer lasting disease control compared to cryoablation alone and lead to a much quicker time to treatment response and symptom relief than nirogacestat alone. Also, there is no risk of secondary malignancy (in comparison to radiation) and we predict that side effects will be more tolerable than chemotherapy and/or VEGF TKIs.

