For the overall outcome:

- SD=Changes not meeting above criteria
- Overall Response (OR)=CR+PR
- CB=CR+PR+D

The outcome is the number of participants with OR per RECIST or mRECIST within 1 year, a number without dispersion.

Time frame: 1 year

- **Outcome 5 (Secondary) Title: Time-to-Response (TTR)**

Description: Time-to-response (TTR) is an assessment of the length of time from the start of treatment until clinical response (complete response, CR; or partial response, PR) is documented.in accordance with the Revised Response Evaluation Criteria in Solid Tumors (RECIST)v1.1, or, for assessed with MRI enhancement, modified RECIST (mRECIST) defined as follows:‘

RECIST v1.1:

- CR=Disappearance of all lesions
- PR= $\geq 30\%$ decrease in diameter of target lesions
- Progressive disease (PD)=20% increase in diameter of target lesion; progression of non-target lesion; or ≥ 1 new lesion(s)

mRECIST:

- CR=Disappearance of intratumoral enhancement
- PR= $\geq 30\%$ decrease in the diameter of target lesion(s)
- PD=An increase of $>20\%$ in the diameter of target lesion.

For either:

- SD=Changes not meeting above criteria

The outcome is expressed as the median TTR (by RECIST or mRECIST), with standard deviation.

Time Frame: 1 year

- **Outcome 6 (Secondary) Title: Duration of Response (DoR)**

Description: Duration of response (DoR) is defined as the time from the date of documented disease response (complete response, CR; or partial response, PR) to the date of the first documented disease progression. CR and PR will be assessed according to the Revised Response Evaluation Criteria in Solid Tumors (RECIST)v1.1, or, for assessed with MRI enhancement, modified RECIST (mRECIST) as follows:

RECIST v1.1:

- CR=Disappearance of all lesions
- PR= $\geq 30\%$ decrease in diameter of target lesions
- Progressive disease (PD)=20% increase in diameter of target lesion; progression of non-target lesion; or ≥ 1 new lesion(s)

mRECIST:

- CR=Disappearance of intratumoral enhancement
- PR= $\geq 30\%$ decrease in the diameter of target lesion(s)
- PD=An increase of $>20\%$ in the diameter of target lesion.

For both:

- SD=Changes not meeting above criteria

The outcome is expressed as the median DoR, with standard deviation. Participants alive with a clinical response and without progression 24 months after treatment will be censored at that time.

Time Frame: 2 year

- **Outcome 7 (Secondary) Title: Related Adverse Events (AEs)**

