For tumors with MRI enhancement, CBR will be evaluated on the basis of clinical response as measured using imaging by MRI scan and evaluated by modified RECIST (Appendix D). Determination of response will be made by the treating investigator. Imaging will be performed at screening, then every 3 cycles (ie, every 12 weeks \pm 14 days) until End of Treatment. MRI scan will be used at screening and at subsequent time points.

10.2.2.2. **Median Progression-free Survival (PFS)**

Median progression free survival (PFS) will be measured using imaging by MRI scan and evaluated by RECIST v1.1, mRECIST, and volumetrically (change in tumor volume as assessed by MRI volumetric).

Progression-free survival is defined as the time from start of treatment to date of progression or death due to any cause. If a subject is not known to have progressed or died, then PFS will be censored at the latest date the subject was known to be alive or progression-free (on or before the cut-off date). The PFS distribution will be estimated using the Kaplan-Meier method, and

the Kaplan-Meier curves, medians and 95% confidence intervals of the medians will be presented.

10.2.2.3. **Objective Response Rate (ORR) at 1 year**

For the objective response rate (ORR) at 1 year, the percentage of subjects who start study treatment and achieve an objective response (CR or PR) will be calculated. ORR will be measured using imaging by MRI scan and evaluated both RECIST v1.1, mRECIST, and MRI volumetric.

The ORR will be calculated as the proportion of subjects with objective response. The ORR and the two-sided 95% Clopper-Pearson (exact) confidence interval will be calculated.

10.2.2.4. **Time to Response (TTR)**

Time to response is defined as the time from the start of treatment with nirogacestat to the first objective tumor response (CR or PR), and will be measured using imaging by MRI scan and evaluated by RECIST v1.1, mRECIST, and volumetrically.

The TTR distribution will be estimated using the Kaplan-Meier method, and the Kaplan-Meier curves, medians and 95% confidence intervals of the medians will be presented.

10.2.2.5. **Duration of Response (DoR)**

Duration of response (DoR) is defined as the time from the date of documented disease response (CR or PR) to the date of the first documented progression, and will be determined using imaging by MRI scan and evaluated by RECIST v1.1, mRECIST, and volumetrically.

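### Time to response is specified for registry reporting with a 1-year frame and a median with SD, while Section 10.2.2.4 sets no time limit and uses Kaplan-Meier

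*Protocol*

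**What the plan says.** Protocol Section 2.3.2.2 lists the secondary outcomes for ClinicalTrials.gov reporting. Outcome 5, TTR, runs from start of treatment to documented CR or PR. Its summary reads "The outcome is expressed as the median TTR (by RECIST or mRECIST), with standard deviation" and its frame is "Time frame: 1 year". It has no censoring rule.

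Outcome 6, duration of response (DoR), directly below it, has "Time Frame: 2 year" and does state a censoring rule: "Participants alive with a clinical response and without progression 24 months after treatment will be censored at that time".

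Section 10.2.2.4 begins "Time to response is defined as the time from the start of treatment with nirogacestat to the first objective tumor response (CR or PR" and gives no upper limit. It specifies Kaplan-Meier curves, medians and 95% confidence intervals. The synopsis and Section 2.2.2 also leave TTR without a limit, although the same lists attach 1 year to the clinical benefit rate and the objective response rate.

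The protocol schema places MRI before Cycles 4, 7, 10, 13, 16, 19, 22 and 25, with treatment for up to 26 cycles.

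On nirogacestat alone, Section 1.1 gives a 1-year objective response rate of 2 of 17 (12%) and 29% overall. Section 1.2.4 reports that "16 subjects were evaluable for response with 5 (29%) subjects achieving PR after a median of 32 cycles (96 weeks) of nirogacestat". Section 1.3.3 hypothesises that the combination will "lead to a much quicker time to treatment response and symptom relief than nirogacestat alone".

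**The concern.** The two parts of the protocol that specify TTR disagree on both the window and the summary. The difference is not only wording. A median with a standard deviation is naturally computed on observed response times, and a 1-year frame caps those times at 12 months whatever the treatment does. Kaplan-Meier without a limit has no such cap.

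There is also a mismatch within the reporting list. DoR starts at the documented response and is followed for 2 years. A response first seen at week 72, for example, could contribute to DoR but would fall outside TTR, so the two outcomes would describe different sets of responders.

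Speed of response is one of the hypothesised advantages of the combination. A posted median that looks shorter only because later responses were left out could be misread as support for that hypothesis.

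**Working it through.** **1. Reproduce the drug-alone figures.** 2/17 = 11.8%, stated as 12%. 5/17 = 29.4%, stated as 29%. The alternative 5/16 = 31.3% does not match, so the denominator is 17.

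**2. Responses after 1 year, drug alone.** 5 − 2 = 3, and 3/5 = 60%. The exact (Clopper-Pearson) 95% CI for 3 of 5 is 15% to 95%. The subtraction assumes that the 1-year rate counts every response up to that point. The 96 weeks in Section 1.2.4 may be time on treatment, so it is not used as a response time.

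**3. Scan calendar.** The scan before Cycle c falls at week 4 × (c − 1):

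| Scan before | C4 | C7 | C10 | C13 | C16 | C19 | C22 | C25 |
|---|---|---|---|---|---|---|---|---|
| Week | 12 | 24 | 36 | 48 | 60 | 72 | 84 | 96 |

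The C13 scan is at day 336, or day 350 at the late edge of the ±14-day window, and so within 1 year. The C16 scan is at day 420, or day 406 at the early edge, and so beyond it. Four of the eight scheduled on-treatment scans therefore cannot date a response under a 1-year frame.

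**4. Effect on a median of observed times, drug-alone pattern.** With five ordered response times the median is the third. Two fall within 1 year, so the third lies beyond 12 months with full follow-up. With the cut, only the first two remain and their median is at most 12 months.

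**5. Expected counts for N = 20 at drug-alone rates (illustration only).** 20 × 5/17 = 5.9 responders in all, 20 × 2/17 = 2.4 by 1 year and 20 × 3/17 = 3.5 later.

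**6. Sensitivity to the late share.** Simulation with N = 20 and response probability 5/17. Response times are spread evenly over the four scans in each year, which is an assumption. Entries are the mean of the responder medians, in weeks, over simulated trials with at least one response in the window:

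| Share of responses after 1 year | Full window | 1-year cut |
|---|---|---|
| 0% | 30 | 30 |
| 20% | 36 | 30 |
| 40% | 47 | 30 |
| 60% | 60 | 30 |

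The cut median barely moves whatever the late share, while the full-window median doubles across the range.

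**7. Kaplan-Meier on all subjects.** At drug-alone rates the cumulative response is 12% at 1 year and 29% at about 2 years. Both are below 50%, so the median is not reached with or without a cut, and the curve to 12 months is the same. A 1-year cut under Kaplan-Meier censors late responders and does not make response look faster.

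**The case against.** The strongest reply is that Outcome 5 never says late responders are dropped or that the median is taken only among first-year responders. The statistical section keeps every response, and the later scans still feed TTR under Section 10.2.2.4, PFS and DoR. This stands for Section 10.2.2.4 and is why the point is confined to the reporting entry. It does not rescue that entry: a 1-year frame, a median with SD and no censoring rule lead most naturally to the capped summary.

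Second, the two frames could be deliberate. Outcome 4 counts objective responses within 1 year, TTR could describe how quickly those occurred, and DoR could follow the same subjects to 24 months. That reading is coherent, but the protocol does not restrict DoR to first-year responders, and the conflict with Section 10.2.2.4 would remain.

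Third, the 3 of 5 is fragile. It is a subtraction on five responders from a study that scanned every 18 weeks. If that grid ran from treatment start (an assumption), scans fell near weeks 18, 36 and 54, and a response arising after week 36 would first be recorded just past 1 year. Here subjects also have cryoablation after Cycle 3, and response is also read on enhancing tissue. The late share could be much smaller. All of this stands.

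A reader might go further and infer that the 1-year frame guarantees the hoped-for faster response than nirogacestat alone. The documents do not support that. The synopsis plans a comparison with historical controls, but the protocol states no drug-alone median TTR and no formal TTR test or decision rule.

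**Conclusion.** The inconsistency is real. Section 2.3.2.2 and Section 10.2.2.4 specify different windows and different summaries for the same outcome, and the reporting entry also uses a shorter frame than its companion DoR.

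If the Outcome 5 median is computed on observed response times, it is capped at 12 months and omits responses first seen at weeks 60, 72, 84 or 96. How far it then departs from a full-window median depends on the late share: nothing at 0%, about 6 weeks at 20% and about 30 weeks at 60%, under the even-spacing assumption. A reader should not take 60% as the expected loss in this trial, nor conclude that the late scans go unused.

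The Kaplan-Meier analysis in Section 10.2.2.4, the primary endpoint and the trial's decision rule are not affected. This is a minor-to-moderate correction to a descriptive secondary outcome. The conclusion rests on the protocol alone. The registry record itself was not available.

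**What to change.** In Section 2.3.2.2, set the Outcome 5 time frame to 2 years, in line with the imaging schedule and Outcome 6. Replace the median with standard deviation by the Kaplan-Meier median with 95% CI, as Section 10.2.2.4 already specifies. TTR and DoR would then cover the same responders. If a 1-year description is also wanted, the cumulative response at 12 months can be read from the same curve.

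The cost is one protocol entry and, if it carries the same text, the matching registry entry. No extra scans, visits or subjects are needed.

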Duration of response will be summarized descriptively. If sufficient data are available the distribution will be estimated using the Kaplan-Meier method, and the Kaplan-Meier curves, medians and 95% confidence intervals of the medians will be presented.

Nominal duration of study involvement is 26 months, with last assessment after about 24 months of treatment.

10.2.2.6. **Adverse events and safety**

Adverse events will be tabulated with frequencies and percentages for grade, severity, status and relationship to study drug or study procedure. The analysis population will include all subjects who have started study treatment. Assessment for safety signals will be from time of consent until 30 days after the last treatment.

10.2.3. **Exploratory Endpoints and Analysis**

10.2.3.1. **Patient-reported outcomes (EQ-5D-3L)**

Summary measures (mean, standard deviation, median, interquartile range) of the EQ-5D-3L survey scores will be calculated for each time point during the duration of the study; scores will graphically depicted at each time point. In addition, we will calculate the difference of the scores at the baseline, time of demonstrated clinical benefit rate, and last follow-up date and report summary statistics. Nominal duration of study involvement is 26 months, with last assessment after about 24 months of treatment.

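### Time to response and duration of response are to be posted as a median with a standard deviation, which is invalid for censored durations and departs from the Kaplan-Meier plan in Section 10

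*Protocol*

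**What the plan says.** The protocol describes the two endpoints in two places.

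**Section 2.3.2.2, the outcomes for registry results reporting.**
- Outcome 5 (TTR): "The outcome is expressed as the median TTR (by RECIST or mRECIST), with standard deviation".
- Outcome 6 (DoR): "The outcome is expressed as the median DoR, with standard deviation". The next sentence reads: "Participants alive with a clinical response and without progression 24 months after treatment will be censored at that time".

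**Section 10.2.2, the analysis plan.**
- 10.2.2.4 (TTR): "The TTR distribution will be estimated using the Kaplan-Meier method", and "medians and 95% confidence intervals of the medians will be presented".
- 10.2.2.5 (DoR): "Duration of response will be summarized descriptively", followed by "If sufficient data are available the distribution will be estimated using the Kaplan-Meier method", again with medians and their 95% confidence intervals.

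Section 10.2.2 names no standard deviation for either endpoint.

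**The concern.** A standard deviation describes the spread of individual, fully observed values. It is not the natural companion of a median, and it says nothing about how precisely the median is known. For DoR there is a harder problem. The protocol itself declares some durations incomplete, and a standard deviation calculated from the recorded times treats each cut-off time as if the response had ended then.

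Section 2.3.2 governs what is posted, and Section 2.3 says results will be reported. Followed as written, the DoR entry would carry a dispersion figure that looks tightest when responses are most durable. Such a figure can also be calculated when the median does not exist. For TTR, the posted summary would differ from the one that the analysis section produces.

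**Working it through.** The plan gives no figure to reproduce here, so the check is a comparison of texts followed by an illustration of size.

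**1. The two places side by side**

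| Endpoint | Section 2.3.2.2 | Section 10.2.2 | Conflict |
|---|---|---|---|
| TTR | Median with standard deviation; no censoring rule stated | Kaplan-Meier median with 95% CI | Outright |
| DoR | Median with standard deviation; censored at 24 months | Unspecified descriptive summary; Kaplan-Meier median with 95% CI if data suffice | Only when the Kaplan-Meier option is used |

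The DoR defect does not depend on Section 10. A standard deviation and censoring are prescribed in adjacent sentences of Section 2.3.2.2.

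**2. What the standard deviation of recorded DoR times would show**

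The documents give no rate of progression after response, so these inputs are all assumptions:
- 8 responders.
- 18 months of follow-up after response, that is, response at 6 months and censoring at 24 months from treatment start.
- Exponential durations with true median m = 12, 24 or 48 months.

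Formulas:
- Probability that a duration is censored: 2^(−18/m).
- With a common cut-off, the Kaplan-Meier curve after k progressions is (8 − k)/8. It reaches 0.5 when k is at least 4, so the probability that the median is reached is P(Binomial(8, 1 − 2^(−18/m)) ≥ 4).
- The standard deviation of the eight recorded times, min(duration, 18), is averaged over simulated trials.

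| True median (months) | Censored | Mean SD of recorded times (months) | Kaplan-Meier median reached |
|---|---|---|---|
| 12 | 2^(−1.5) = 35% | 6.4 | 89% |
| 24 | 2^(−0.75) = 59% | 5.5 | 42% |
| 48 | 2^(−0.375) = 77% | 4.0 | 9% |

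As the true median rises fourfold, the reported spread falls. The true spread of an exponential distribution is proportional to its median and would rise fourfold. At a median of 48 months, all eight durations are censored with probability (2^(−0.375))^8 = 2^(−3) = 12.5%. The standard deviation would then be exactly zero, with no median to accompany it.

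**3. Sensitivity to the follow-up assumption**

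Let responses instead occur evenly between 3 and 12 months, with censoring at 24 months from treatment start and 6, 8 or 12 responders. The mean standard deviation is then about 6, 5.4 and 4.4 months for the three true medians. The Kaplan-Meier median is not reached in 12–16%, 55–61% and 85–92% of trials. The pattern is the same.

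**4. TTR**

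Assume all 20 evaluable subjects enter the Kaplan-Meier estimate and none is censored early. The median then exists only if at least 10 respond, with probability P(Binomial(20, p) ≥ 10). For p I take two nirogacestat-alone rates from the protocol and one assumed rate:
- 12% (2 of 17 at 1 year, Section 1.1): below 0.01%.
- 41% (phase 3, Section 1.2.4): 27%.
- 50% (assumed): 59%.

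The TTR entry therefore also needs room for a median that is not reached.

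**The case against.** The strongest reply is that Section 2.3.2 speaks the registry's language of dispersion. Several of its count outcomes are described as having none, so the standard deviation may be meant as spread and not as the precision of the median. That stands: the protocol nowhere offers it as an error bar. It does not rescue DoR, because spread cannot be taken from censored times either.

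A reader might infer more than the documents support in four ways.

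- **That Section 10 flatly contradicts the DoR wording.** It does not. Section 10.2.2.5 begins with an unspecified descriptive summary and turns to Kaplan-Meier only if data suffice. The conflict is unconditional for TTR alone.
- **That TTR is declared censored in Section 2.3.2.2.** Only DoR is. For TTR, censoring follows from the Kaplan-Meier method in 10.2.2.4. If TTR were summarised among responders only, every time would be observed and a standard deviation could be calculated. Neither section names that population.
- **That the harm is the gap between the recorded and the true standard deviation.** The true value depends on a tail far beyond the follow-up limit, and a Kaplan-Meier median with its interval does not estimate it either. Nor can a progression rate after response be taken from the alternative clinical benefit rate of 0.8 in Section 10.4.2. That rate is a proportion at 1 year from treatment start and includes stable disease.
- **That DoR is wrong to end at progression only because PFS also counts death.** Sections 2.2.2, 2.3.2.2 and 10.2.2.5 all end DoR at progression. Two endpoints with different events are not a contradiction, and no material effect is shown.

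**Conclusion.** The point holds. The DoR wording prescribes an invalid statistic for an outcome that the same section censors. The TTR wording conflicts with Section 10.2.2.4, and the DoR wording conflicts with Section 10.2.2.5 whenever Kaplan-Meier is used. That DoR is censored and that the sections differ can be read directly from the text. The sizes rest on assumed numbers of responders, follow-up and exponential durations, and serve only to show the direction: the reported spread falls, and the median is reached less often, as responses last longer.

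The reach is limited to the reporting of two secondary outcomes. The primary endpoint, sample size and error rates are untouched. The wording should be corrected before results are posted.

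**What to change.** - In Outcomes 5 and 6 of Section 2.3.2.2, replace the median with standard deviation by: Kaplan-Meier median with 95% CI (not reached if not estimable). This matches Section 10.2.2.4 and the Kaplan-Meier option in 10.2.2.5.
- Where DoR data are too few for Kaplan-Meier, report the individual durations, or their range, with censored values marked. Say so in both 2.3.2.2 and 10.2.2.5, so that the descriptive summary is no longer unspecified.
- Align the registry entry if it carries the same wording.

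The cost is a wording change. It needs no extra data, visits or subjects and alters no endpoint definition.
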